4.3.2. Adherence with Blinded Study Drug Regimen

Study drug regimen adherence will be computed based on tablet counts for the active drug only (eg, adherence in TAF group only includes TAF and not placebo for TDF). The numbers of tablets of study drug dispensed and returned are captured on study drug accountability forms.

Adherence (%) of study drug regimen will be calculated as follows:

$$\begin{aligned}\text{Adherence (\%)} &= 100 \times \frac{\text{Number of tablets taken}}{\text{Number of tablets prescribed}} \\ &= 100 \times \frac{\sum \text{No. of tablets taken at each dispensing period [1]}}{\sum \text{No. of tablets prescribed at each dispensing period [2]}}\end{aligned}$$

- [1] Number of tablets taken at a distinct dispensing period for a study drug is calculated as the minimum of (a) the daily number of tablets prescribed for the study drug multiplied by **the duration of treatment** at the dispensing period of the same dispensing date, and (b) the number of tablets taken for the study drug (number of tablets dispensed minus the number of tablets returned). Total number of tablets taken is determined by summing the number of tablets taken from all evaluable dispensing periods.
- [2] Number of tablets prescribed at a distinct dispensing period for a study drug is calculated as the daily number of tablets prescribed for the study drug multiplied by **the duration of treatment** at the dispensing period of the same dispensing date. Total number of tablets prescribed is determined by summing the number of tablets prescribed from all evaluable dispensing periods.

The duration of treatment at a dispensing period for a study drug is calculated as the minimum of (a) the last returned date of the same dispensing period for the study drug, (b) date of premature discontinuation of the study drug, and (c) **next dispensing date** of the study drug, minus dispensing date of the study drug.

The next dispensing date is the following dispensing date of the study drug regardless of the bottle return date.

For a record where the number of tablets returned was missing (with “Yes” answered for “Was bottle returned?” question), it is assumed the number of tablets returned was 0. If the number of tablets dispensed was missing or any study drug bottle was not returned or the bottle return status was unknown for the same dispensing date, then all records for the same dispensing date for that study drug will be excluded from both denominator and numerator calculation.

Adherence up to Week 48 visit will be calculated for each subject.

The number and percentage of subjects who return at least 1 bottle and have calculable adherence during the study, descriptive statistics for adherence up to Week 48 visit for a study drug regimen (sample size, mean, SD, median, Q1, Q3, minimum, and maximum) along with the number and percentage of subjects belonging to adherence categories (eg, < 80%, ≥ 80% to < 90%, ≥ 90% to < 95%, ≥ 95%) will be provided by treatment group for the Safety Analysis Set.

4.4. Protocol Deviations

A listing will be provided for subjects in the Randomized Analysis Set who violated at least 1 inclusion or exclusion criterion. The listing will include the unmet criteria. A listing of subjects who received the wrong study treatment will also be provided.

5. BASELINE CHARACTERISTICS

5.1. Demographics and Baseline Characteristics

Subject demographic data (eg, age, sex) and baseline characteristics (eg, body weight, height, body mass index [BMI], and Vitamin D) will be summarized by treatment group and overall using descriptive statistics (sample size, mean, SD, median, Q1, Q3, minimum, and maximum) for continuous data and by the number and percentage of subjects for categorical data. Age is calculated as age in years at the first dose of study drug. The summaries of demographic data and baseline subject characteristics will be provided for the Safety Analysis Set.

In addition, the following baseline characteristics and medical history will be summarized:

- BMI categories ($< 18.5 \text{ kg/m}^2$ [underweight], $\geq 18.5 - 25.0 \text{ kg/m}^2$ [normal], $\geq 25.0 - 30.0 \text{ kg/m}^2$ [overweight], and $\geq 30.0 \text{ kg/m}^2$ [obese])
- HBV DNA (\log_{10} IU/mL)
- HBV DNA categories ($< 7 \log_{10}$ IU/mL, $\geq 7 \log_{10}$ IU/mL - $< 8 \log_{10}$ IU/mL, $\geq 8 \log_{10}$ IU/mL)
- ALT (U/L)
- ALT level based on central laboratory normal range ($\leq \text{ULN}$, $> \text{ULN} - 5 \times \text{ULN}$, $> 5 \times \text{ULN} - 10 \times \text{ULN}$, $> 10 \text{ ULN}$)
- ALT level based on American Association for the Study of Liver Diseases (AASLD) normal range with the ULN as 19 U/L for female and 30 U/L for male ($\leq \text{ULN}$, $> \text{ULN} - 5 \times \text{ULN}$, $> 5 \times \text{ULN} - 10 \times \text{ULN}$, $> 10 \text{ ULN}$)
- Estimated GFR by CG, CKD-EPI creatinine, and CKD-EPI Cystatin C methods
- HBeAg status (positive, negative)
- HBeAb status (positive, negative)
- Previous oral nucleoside/nucleotide treatment experience (yes, no)
- Previous interferon experience (yes, no)
- Years positive for HBV
- HBV Genotype (A, B, C, D, E, F, etc)
- Fibrotest score

- Fibrosis stage by fibrotest score (0 - 0.48, 0.49 - 0.74, 0.75 - 1)
- Cirrhosis history (yes, no, indeterminate/unknown)
- Proteinuria by urinalysis (dipstick) (Grade 0, Grade 1, Grade 2, Grade 3)
- Medical history: diabetes mellitus (yes, no), hypertension (yes, no), cardiovascular disease (yes, no), and hyperlipidemia (yes, no)
- Clinical BMD status (normal, osteopenia, osteoporosis)
- Hip fracture and major osteoporotic fracture probabilities estimated using FRAX[®] (see Section 7.3.4)
- IL28B Genotype

Diabetes mellitus, hypertension, cardiovascular disease, and hyperlipidemia above are determined by medical history and/or concomitant medication data, which will be reviewed by the Gilead medical monitor before unblinding.

5.2. Medical History

A listing of medical history data will be provided for the Randomized Analysis Set.

6. EFFICACY ANALYSES

For the Week 48 analyses, efficacy data will be summarized for the double-blind phase up to Week 96), with the exception that summaries using M = F approach will be presented up to Week 48 only. All efficacy data up to the Week 48 data-cut including data collected during open-label phase and 24-week treatment-free follow-up period will be listed.

6.1. Primary Efficacy Endpoints

6.1.1. Definition of the Primary Efficacy Endpoint

The primary efficacy endpoint is the proportion of subjects with HBV DNA < 29 IU/mL at Week 48.

6.1.2. Analysis of the Primary Efficacy Endpoint

The primary efficacy analysis will be conducted after the last randomized subject reaches Week 48 or discontinues study drug prematurely. An M = F approach will be employed. In this approach, all missing data will be treated as not achieving the primary endpoint (ie, having HBV DNA \geq 29 IU/mL). The primary analysis will use the FAS.

The number and percentage of subjects who achieved and did not achieve HBV DNA < 29 IU/mL, and reasons for no HBV DNA data at Week 48 will be summarized.

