8.5.2. Analyses of Other Endpoints of Interest

Continuous secondary endpoints will be summarized using conventional descriptive statistics (n, mean, standard deviation, median, Q1, Q3, minimum, and maximum) by treatment group and overall. A Wilcoxon rank sum test will be used to compare the treatment groups, in an exploratory manner.

Categorical secondary endpoints will be summarized by number and percentage of subjects that meet the endpoint. A two-sided Mantel-Haenszel test, controlling for the randomization strata, will be used to compare the treatment groups, in an exploratory manner. Missing data will be handled by the missing = failure approach.

For the incidence of drug resistant mutations, the missing = excluded approach will be employed.

An analysis of the China subpopulation will also be conducted when approximately 150 randomized and treated China subjects complete 48 weeks of double-blind treatment or discontinue prematurely to examine the consistency of the responses between the China subpopulation and the overall population.

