1.1. Study Objectives

The primary objectives of this study are as follows:

- To compare the efficacy of TAF 25 mg versus TDF 300 mg once daily for the treatment of hepatitis B e antigen (HBeAg)-negative, CHB at Week 48 in treatment-naïve and treatment-experienced subjects. The primary efficacy parameter is the proportion of subjects with plasma HBV DNA levels below 29 IU/mL
- To compare the safety and tolerability of TAF 25 mg once daily versus TDF 300 mg once daily for the treatment of HBeAg-negative, CHB at Week 48 in treatment-naïve and treatment-experienced subjects

The key secondary safety objectives of this study are as follows:

- To compare the safety of TAF 25 mg once daily versus TDF 300 mg once daily as determined by the percent change from baseline in hip and spine bone mineral density (BMD) at Week 48
- To compare the safety of TAF 25 mg once daily versus TDF 300 mg once daily as determined by the change from baseline in serum creatinine at Week 48
- To compare the safety of TAF 25 mg once daily versus TDF 300 mg once daily as determined by treatment-emergent proteinuria through Week 48

Other secondary objectives of this study are as follows:

- To compare the efficacy of TAF 25 mg once daily versus TDF 300 mg once daily for the treatment of HBeAg-negative, CHB in regard to the proportion of subjects with plasma HBV DNA levels below 29 IU/mL at Week 96, and 144
- To compare the efficacy of TAF 25 mg once daily versus TDF 300 mg once daily for the treatment of HBeAg-negative, CHB in regard to the proportion of subjects with plasma HBV DNA levels below 29 IU/mL (target not detected) at Weeks 48, 96, and 144
- To compare the biochemical (alanine aminotransferase [ALT] normalization) response of TAF 25 mg once daily versus TDF 300 mg once daily for the treatment of HBeAg-negative, CHB at Weeks 48, 96, and 144
- To compare the serological response (loss of hepatitis B surface antigen [HBsAg] with seroconversion to antibody to HBsAg [anti-HBs]) of TAF 25 mg once daily versus TDF 300 mg once daily for the treatment of HBeAg-negative, CHB at Weeks 48, 96, and 144
- To compare the change in fibrosis as assessed by FibroTest[®] of TAF 25 mg once daily versus TDF 300 mg once daily for the treatment of HBeAg-negative, CHB at Weeks 48, 96, and 144
- To compare the incidence of drug resistant mutations of TAF 25 mg once daily versus TDF 300 mg once daily at Weeks 48, 96, and 144

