2. TYPE OF PLANNED ANALYSIS

The Week 48 analysis for Non-China subjects was already conducted after the last subject completed the Week 48 visit or prematurely discontinued study drug. This statistical analysis plan (SAP) describes the analysis plan for the Week 48 analysis of subjects enrolled in China only.

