2.2. Week 48 Analysis (Primary Analysis)

The Week 48 analysis will be conducted after the last subject completes the Week 48 visit or prematurely discontinues study drug.

Further analyses after Week 48 will be conducted if warranted.

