3.3. Strata and Covariates

Randomization was stratified by plasma HBV DNA level ($< 7 \log_{10}$ IU/mL, $\geq 7 \log_{10}$ IU/mL - $< 8 \log_{10}$ IU/mL, $\geq 8 \log_{10}$ IU/mL) and oral antiviral treatment status (treatment-naïve vs treatment-experienced) at screening. HBV DNA strata will be reclassified using baseline HBV DNA level for stratified statistical analysis.

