6.1.4. Subgroup Analysis for the Primary Efficacy Endpoint

The analysis of proportion of subjects who achieved HBV DNA < 29 IU/mL at Week 48 will be repeated within each subgroup specified in Section 3.4 using FAS.

For each level of subgroup factors, the number and percentage of subjects who achieved HBV DNA < 29 IU/mL at Week 48 will be summarized.

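### The China Week 48 SAP plans only counts and percentages by arm for the primary endpoint, so it does not prespecify how the consistency named in Protocol 8.5.2 will be estimated

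*SAP*

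**What the plan says.** SAP section 2 sets the scope: "This statistical analysis plan (SAP) describes the analysis plan for the Week 48 analysis of subjects enrolled in China only". The heading of SAP 2.2 labels the Week 48 analysis as primary. The first primary objective in SAP 1.1 is comparative: it sets the efficacy of TAF against that of TDF at Week 48.

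For the primary endpoint, SAP 6.1.2 specifies the FAS, the M = F rule and this output: "The number and percentage of subjects who achieved and did not achieve HBV DNA < 29 IU/mL", with reasons for absent Week 48 data. SAP 6.1.3 repeats the proportion under M = E and in the per-protocol set. For subgroups, SAP 6.1.4 says that "the number and percentage of subjects who achieved HBV DNA < 29 IU/mL at Week 48 will be summarized". No title in Appendix 1 refers to a treatment difference or to non-China or overall results.

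SAP 3.3 says "HBV DNA strata will be reclassified using baseline HBV DNA level for stratified statistical analysis", but section 6 defines no stratified analysis.

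On the protocol side, 8.5.1 defines the primary comparison as a two-sided 95% CI for TAF minus TDF, using Mantel-Haenszel proportions adjusted for the randomization factors. Protocol 8.5.2 adds a China analysis "to examine the consistency of the responses between the China subpopulation and the overall population" and prescribes no method for it.

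**The concern.** A plan whose objective is to compare two arms should say what quantity does the comparing and how uncertain it is. Here the output is two percentages. Any statement that the Chinese results agree with the rest of the trial would rest on a reader's impression of four response rates, two from China and two from the earlier cohort.

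Two features make this more than a matter of presentation. First, SAP section 2 says that the non-China Week 48 analysis has already been done. An unspecified consistency assessment therefore leaves the choice of measure open after one side of the comparison is known. Second, the arms are small. One subject in the planned TDF arm of 50 is worth 2 percentage points, so five subjects move that rate by 10 points, the size of the protocol's non-inferiority margin. Percentages without an interval for their difference hide this.

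The text also suggests that a comparative method was once intended or expected. Strata are prepared and not used. The abbreviation list includes MH, CMH, ANOVA and ANCOVA, which no analysis section uses. SAP 6.2.2 describes the statistical method of the primary analysis as M = F, which is a missing-data rule and not a method of comparison.

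**Working it through.** **Inputs**

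- China: about 100 TAF and 50 TDF (SAP 1.2 and 1.3).
- Non-China: 285 TAF and 141 TDF (SAP 1.2).
- Planning rate: 91% in both arms (Protocol 8.8). For China this is an assumption, because the documents give no China rate, so a range is shown.
- Margin 10 points, one-sided 0.025 (Protocol 8.8).

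**Reproducing the plan's own figure.** For the powered comparison of 130 TDF with 260 TAF:

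SE = √[0.91 × 0.09 × (1/130 + 1/260)] = 0.0307

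Power = Φ(0.10/0.0307 − 1.96) = 90.2%

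The stated 90% is reproduced, so the same unpooled normal approximation is used below.

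**Precision of the China difference**

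SE = √[0.91 × 0.09 × (1/100 + 1/50)] = √0.002457 = 0.0496

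95% half-width = 1.96 × 0.0496 = 9.7 points

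**Precision of the China versus non-China contrast.** The cohorts are independent, so their variances add.

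Non-China SE = √[0.91 × 0.09 × (1/285 + 1/141)] = 0.0295

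Contrast SE = √(0.0496² + 0.0295²) = 0.0577

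95% half-width = 1.96 × 0.0577 = 11.3 points

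**Range over the assumed common rate**

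| Rate in both arms | China TAF-TDF half-width | China minus non-China half-width |
|---|---|---|
| 85% | 12.1 points | 14.1 points |
| 91% | 9.7 points | 11.3 points |
| 95% | 7.4 points | 8.6 points |

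All of these are unstratified approximations. A stratified interval will differ somewhat.

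**What a margin test would do in China.** Power = Φ(0.10/0.0496 − 1.96) ≈ 52% at 91%. That is a reason to present an estimate and not a non-inferiority verdict.

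**The case against.** The strongest reply is that a descriptive China analysis looks deliberate. The cohort was added for local registration, SAP 1.3 limits the power calculation to non-China subjects, and the China SAP is descriptive elsewhere too: BMD and creatinine are summarized in SAP 7.3.1 and 7.4.2 without the ANOVA and ANCOVA of Protocol 8.6.1. This stands as an argument against a formal test. It does not argue against showing an estimate with its precision, and the SAP nowhere says that a descriptive analysis was chosen or why.

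A reader might also infer any of four stronger claims, which the documents do not support.

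- *That the SAP contains no confidence intervals.* SAP 6.2.2 plots the proportion below 29 IU/mL and mean changes over time with 95% CIs on observed data, and Appendix 1 lists figures of means with 95% CIs. What is missing is an interval for the difference between arms.
- *That consistency cannot be assessed at all.* Protocol 8.5.2 speaks of responses, and rates by randomized arm address that wording descriptively. A crude difference and interval can be worked out from Table 12.
- *That the protocol's primary method was dropped without declaration.* The interval in Protocol 8.5.1 belongs to the analysis triggered at approximately 390 subjects, and the China subjects are additional to these. Whether it was meant to apply to China is arguable, so the silence of SAP 6.3 is not an established deviation.
- *That no comparison is planned anywhere.* This SAP covers China only, and the non-China plan and study report are not available here.

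**Conclusion.** The gap is real and limited. For its primary endpoint the China SAP names no estimate of the treatment difference, no interval for it and no comparison with the other cohort. It therefore leaves unspecified how the consistency in Protocol 8.5.2 will be estimated. At the 91% planning rate, the uncertainty left undisplayed is about ±9.7 points for the China difference and about ±11.3 points for the contrast of treatment effects. Over assumed rates of 95% to 85%, these run from 7.4 to 12.1 and from 8.6 to 14.1 points.

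The figures rest on equal rates in the two arms, the planned China numbers and no stratification. No data are lost and the powered non-China comparison is unaffected, so this is a should-fix point.

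One term also needs defining. The protocol does not say whether the overall population includes the China subjects. If it does, about 150 of 576 subjects (426 + 150), or 26%, would be on both sides of the comparison, and the simple addition of variances used above would not apply.

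**What to change.** 1. In SAP 6.1.2 and Table 12, add the TAF-TDF difference in the China FAS under M = F with a two-sided 95% CI, Mantel-Haenszel adjusted for the randomization factors as in Protocol 8.5.1. This also gives the strata of SAP 3.3 a use. Label it as estimation and not as a powered non-inferiority test.
2. Three HBV DNA levels by two treatment-status levels give six strata, or 150/6 = 25 subjects each on average. The documents give no China stratum counts. State that HBV DNA is collapsed to < 7 versus ≥ 7 log10 IU/mL, already a subgroup cut in SAP 3.4, only if strata are sparse, and define sparse before unblinding.
3. Add one table with arm rates and differences for China and non-China side by side, and for the pooled population if that is what the protocol means by overall. Include the difference between the China and non-China treatment effects with its 95% CI. If the sponsor wants a rule for calling results consistent, it should be written here.
4. In SAP 6.3, state how this analysis relates to Protocol 8.5.1 and 8.5.2.

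The cost is SAP wording and one or two tables, since the non-China Week 48 analysis has already been conducted. The downside is that the intervals will be visibly wide.

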6.1.3. Secondary Analysis for the Primary Efficacy Endpoint

A Missing = Excluded (M = E) approach will be used to summarize proportion of subjects with HBV DNA < 29 IU/mL by visit. In this approach, all missing data will be excluded in the computation (ie, missing data points will be excluded from both the numerator and denominator in proportion computation).

A secondary analysis based on the Week 48 PP analysis set will also be performed to evaluate the robustness of the primary analysis of the primary endpoint.

6.1.4. Subgroup Analysis for the Primary Efficacy Endpoint

The analysis of proportion of subjects who achieved HBV DNA < 29 IU/mL at Week 48 will be repeated within each subgroup specified in Section 3.4 using FAS.

For each level of subgroup factors, the number and percentage of subjects who achieved HBV DNA < 29 IU/mL at Week 48 will be summarized.

6.2. Secondary Efficacy Endpoints

6.2.1. Definition of Secondary Efficacy Endpoints

The secondary efficacy endpoints are as follows:

- The proportion of subjects with plasma HBV DNA < 29 IU/mL at Weeks 96, 144, 240, and 384
- The proportion of subjects with plasma HBV DNA < 29 IU/mL (target not detected) at Weeks 48, 96, 144, 240, and 384
- The proportion of subjects with ALT normalization (by central laboratory and AASLD criteria) at Weeks 48, 96, 144, 240, and 384
- The proportion of subjects with HBsAg loss at Weeks 48, 96, 144, 240, and 384
- The proportion of subjects with HBsAg seroconversion to anti-HBs at Weeks 48, 96, 144, 240, and 384
- The change from baseline in fibrosis as assessed by FibroTest[®] at Weeks 48, 96, 144, 240, and 384
- The incidence of drug resistant mutations at Weeks 48, 96, 144, 240, and 384
- The change from baseline in log₁₀ (HBV DNA) (IU/mL) at Weeks 48, 96, 144, 240, and 384
- The change from baseline in log₁₀ (HBsAg) (IU/mL) at Weeks 48, 96, 144, 240, and 384
- The change from baseline in ALT at Weeks 48, 96, 144, 240, and 384

The secondary endpoints beyond Week 96 (Weeks 144, 240, and 384) will not be summarized for the Week 48 analysis. Incidence of drug resistant mutations will be reported in a separate virology report.

For the Week 48 analysis, the following definitions will be used:

- HBsAg loss is defined as HBsAg test result changes from HBsAg positive at baseline to HBsAg negative at a postbaseline visit with baseline HBsAb negative or missing
- HBsAg seroconversion is defined as HBsAg loss and HBsAb test result changes from HBsAb negative or missing at baseline to HBsAb positive at a postbaseline visit
- ALT normalization is defined as ALT > ULN (by central laboratory normal range or AASLD normal range) at baseline but within normal range at a postbaseline visit

Both baseline and postbaseline borderline serology results will be imputed using the following rules:

- HBsAg and HBeAg borderline will be considered as HBsAg positive and HBeAg positive
- HBsAb and HBeAb borderline will be considered as HBsAb negative and HBeAb negative

6.2.2. Analysis Methods for Secondary Efficacy Endpoints

The analyses for the secondary efficacy endpoints will be conducted using the FAS.

All the secondary efficacy endpoints involving proportions will be analyzed using the same statistical method ($M = F$) applied to the analysis of the primary efficacy endpoint. Sensitivity analyses will be performed using the $M = E$ approach as well.

The change from baseline in \log_{10} (HBV DNA) (IU/mL), \log_{10} (HBsAg) (IU/mL), and ALT will be summarized by visit using observed data (ie, missing will be excluded). In addition, the proportion of subjects with HBV DNA < 29 IU/mL, mean change from baseline in \log_{10} (HBV DNA) (IU/mL), \log_{10} (HBsAg) (IU/mL), and ALT (U/L) will be plotted with 95% CI over time using observed data for FAS.

Fibrosis assessed by FibroTest[®] at each visit and the change from baseline in fibrotest score will be summarized using descriptive statistics (sample size, mean, SD, median, Q1, Q3, minimum, and maximum) by treatment group. A shift table of fibrosis stage based on fibrotest score by visit will also be provided. Mean change from baseline in fibrotest score will be plotted with 95% CI over time using observed data for FAS. A listing of fibrosis assessment by FibroTest[®] will also be provided.

